To describe the evolution of HIV parameter during treatment (CD4 count and HIV-RNA)	- Median (+IQR) of log HIV RNA at D0 and PT12 - Median (+IQR) of CD4 and CD8 cell counts (absolute count, percentage and CD4/CD8 ratio) at D0 and PT12. - Number of AIDS-defining clinical or biological events using CDC classification (95% CI).
Safety assessment	
To describe all the clinical and biological events occurring during the study course	Number of adverse clinical and biological events that occur during the treatment and up to 48 weeks after the end of the treatment (95% CI).

Methodology

Non-randomized, single arm, multicenter, open-label, Phase IIb pilot study conducted in France

Estimated enrolment 30 patients

Study population

Inclusion criteria

1. Adult ≥ 18 years.
2. A recent acute HCV infection or reinfection (see definition below) occurred within 6 months prior screening:

An acute HCV infection is defined by:

- a. HCV RNA was detectable within 6 months after a negative HCV RNA or HCV serology test.

OR

- b. Detectable HCV RNA and an acute clinical hepatitis occurred within 5 months prior to the screening visit.

Clinical Hepatitis is defined by:

- ALT ≥ 250 IU/L with normal ALT within the preceding 8 months,

or

- ALT ≥ 500 IU/L with either no measured ALT or with abnormal ALT within the preceding 8 months.

OR

- Patients having reported a risk factor for HCV contamination (traumatic sexual intercourse, intranasal, rectal or intravenous drug use) inferior or equal to 6 months.

HCV reinfection is defined by:

- a. Documented *de novo* infection after prior clearance after treatment or spontaneously,
 - After-treatment clearance is defined by one negative HCV RNA ≥ 6 months after end of treatment.
 - Spontaneous clearance is defined by two negative HCV RNA a minimum of 6 months apart.

OR

- b. Documented infection with a new viral strain, confirmed by phylogenetic or genotypic analysis.

3. Infection with HCV genotype 1 or 4 (confirmed at screening visit or by using a previous biological test performed 1 to 4 weeks before D0).
4. Plasma HCV-RNA ≥ 1000 IU/mL (confirmed at screening visit or by using a previous biological test performed 1 to 4 weeks before D0).
5. Confirmed HIV infection (only for HIV co-infected patients).
6. Without HIV treatment or with an authorized stable HIV treatment for at least two weeks (See section 8.3 of the protocol, only for HIV co-infected patients).
7. Body weight ≥ 40 kg and ≤ 125 kg.

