- To assess the emergence of resistance in case of virological failure (HCV RNA \geq 12 IU/mL).
- To describe treatment adherence and quality of life during the course of the study.
- To evaluate the incidence of HCV reinfection at 1 year (PT48).
- To evaluate the sensitivity of HCV rapid testing (using the Oraquick HCV rapid antibody test) in patients with first acute Hepatitis C.

HIV virological assessment (only for HIV co-infected patients)

- To describe the evolution of HIV parameter during treatment (CD4 count and HIV-RNA).

Safety assessment

- To describe all the clinical events occurred during the study course

5 **METHODOLOGY**

5.1 **General design of the research**

Non-randomized, single arm, multicenter, open-label, Phase IIb pilot study conducted in France.

5.2 **Research milestones**

- Trial start date: Beginning 2017
- Enrolment period: 9 months
- Subject participation duration: screening (1 to 3 weeks before D0), then 56 weeks of follow-up → approximately 60 weeks maximum
- Total trial duration: 24 months
- Estimated study completion date: Beginning 2019

The end of the trial corresponds to the date of the last visit of the last patient.

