10.1.3 Serious Adverse Event/Reaction (SAE/SAR)

A serious adverse event refers to any untoward medical occurrence or effect that at any dose:

- results in death,
- is life-threatening,
- results in persistent or significant disability or incapacity,
- requires hospitalization or prolongation of existing hospitalization,
- is a congenital anomaly or birth defect,
- is a grade 4 clinical adverse event,
- is a grade 4 biological adverse event,
- is an "important medical event" (medical events, based upon appropriate medical judgment, which may jeopardize the subject or may require medical or surgical intervention to prevent one of the above characteristics/consequences).

Examples: allergic bronchospasm requiring intensive treatment at an emergency room or at home, blood dyscrasias, convulsions that do not result in inpatient hospitalization, suspected transmission of an infectious agent via a medicinal product...

EXCEPTIONS:

- medical or surgical procedures (e.g. : *surgery, endoscopy, tooth extraction, transfusion*); only the condition that leads to the procedure should be notified if the condition is referring to a seriousness criteria described above.
- pre-existing diseases or present conditions or detected prior to start of study drug administration, that do not worsen.
- situations where an untoward medical occurrence has not occurred (e.g. : *hospitalization for elective surgery if known prior to start study, social and/or convenience admissions, pre-specified study hospitalizations for observation*).
- grade 4 biological adverse events detected at the screening visit and proven to be pre-existing events (e.g. previous biological results) and those detected prior to start of study drug administration: those must be solely reported in the CRF AE form.
- outpatient care; the patient has been formally admitted to a hospital for medical reasons with no seriousness criteria (described above) and does not require overnight hospitalization.

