10.2 Responsibilities of the Investigator**10.2.1 Timelines**

The investigator has to notify to the sponsor all Serious Adverse Events (SAE) occurring in the trial, **as soon as he becomes aware of it**, except those that the protocol identifies as not requiring immediate reporting (see section 10.1.3).

The immediate report must include the minimum information following: the identifiable coded subject, the identifiable reporter, one suspect medicinal product and one AE.

The immediate report shall be followed, if needed, by complementary detailed reports. The investigator ensures that all relevant information is forwarded to the sponsor within 8 days after the initial notification.

The investigator must follow the subject until clinical recovery is complete and laboratory results have returned to normal or baseline, or until the event has stabilized. Follow-up should continue after completion of protocol treatment if requested.

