10.2.2 Notification period

All serious or not serious adverse events must be reported if they occur:

- From the time the subject signed the study-specific informed consent,
- Until 30 days following the end of study treatment.

Serious adverse events occurring to a subject after the treatment of that subject has ended should be reported to the sponsor if the investigator becomes aware of them. The investigator does not need to actively monitor subjects for adverse events once the trial has ended.

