10.2.4 Notification procedure

AE notification

Grade 1, 2 and 3 biological events and all other AE/AR have to be reported in the proper CRF AE form, except those detected prior to start of study drug administration. If a clinical or biological event is present at inclusion, only its aggravation will be notified.

SAE notification

All SAE/SAR has to be notified by the investigator to the sponsor, immediately as soon as he becomes aware of it, using SAE notification forms, (initial and complementary forms), dated and signed, with due care being paid to the grading, causality and expectedness of the event.

All SAE/SAR should be recorded by the investigator, in corresponding form of the CRF.

When the SAE notification form is filled in, the investigator sends it to the MMC, by [contact] or by email: [contact] and [contact]

Concerning SAE notification forms filling:*The serious adverse event:*

The investigator should assess, if possible, the **diagnosis** of all SAE/SAR.

Diagnosis, or if not available, syndrome should be reported whenever possible.

When several symptoms are linked together (to one pathology), they will not be reported as additional adverse events (e.g. pancreatitis and abdominal pain) but they will be reported on one SAE notification form.

Event onset date :

Date of “event onset” on SAE notification form should be earlier (or the same day) than date of seriousness, and should correspond to the “start date” of the event on the corresponding AE form.

Event outcome:

SAE outcome (which actually corresponds to event outcome) at the time of reporting should be provided on the initial SAE notification form.

Any change in the initial outcome (e.g. resolved, back to previous status, worsening...) should be reported using complementary reporting form(s), outcome on the initial reporting form should not be modified. As long as the adverse event is not resolved, any new worsening will be reported using complementary forms of the corresponding initial SAE.

If the outcome of the event is “resolved”: the date of resolution corresponds to the date of the AE resolution and not of the end of seriousness. “Stop date of seriousness” can be reported on AE form, when the event is no longer considered as serious.

If the outcome of the event is “back to previous status” or “improvement”, the date of event outcome corresponds to the end of seriousness.

The investigational medicinal product:

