13.9 Secondary endpoints

HCV virological assessment

- Median (+IQR) of log HCV RNA at W4, W8, PT4 and PT12, globally and according to genotypes.
- Rate of HCV RNA (<12 IU/mL) at W4, W8, PT4 and PT12, globally and according to genotypes.
- Odds ratio of factors associated with SVR12.
- Number of HCV (NS5A and NS3/4) resistance mutations in patients with virological failure.
- Rate of adherence and quality of life measured by specific scales using self questionnaires.
- Number of patients with positive HCV RNA per hundred months follow-up.

HIV virological assessment

- Median (+IQR) of log HIV RNA at D0 and PT12
- Median (+IQR) of CD4 and CD8 cell counts (absolute count, percentage and CD4/CD8 ratio) at D0 and PT12.
- Number of AIDS-defining clinical or biological events using CDC classification (95% CI).

Safety assessment

- Number of adverse clinical and biological events that occur during the treatment and up to 48 weeks after the end of the treatment (95% CI).

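### The safety endpoint counts adverse events to 48 weeks after treatment, but full adverse event collection is required only to day 30

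*Combined protocol and SAP*

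**What the plan says.** **Endpoint.** The synopsis, 6.2 and 13.9 give the same safety endpoint: "Number of adverse clinical and biological events that occur during the treatment and up to 48 weeks after the end of the treatment", with a 95% CI. The safety objective in the synopsis is "To describe all the clinical and biological events occurring during the study course"; its counterpart in 4.2 is "To describe all the clinical events occurred during the study course".

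**Collection period.** Section 10.2.2 requires reporting of serious and non-serious events from consent and "Until 30 days following the end of study treatment". The adverse event rows in sections 2 and 9.1 carry the same limit. They are marked at screening, D0, W4, W8 and PT4, and not at PT12 or PT48.

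**Serious events later on.** Section 10.2.1 states, without a 30-day limit: "The investigator has to notify to the sponsor all Serious Adverse Events (SAE) occurring in the trial". The list of seriousness criteria in 10.1.3 includes an event that "is a grade 4 biological adverse event". For serious events after a patient's treatment has ended, 10.2.2 says that they "should be reported to the sponsor if the investigator becomes aware of them". Its next sentence releases investigators from active monitoring once the trial is over, and 5.2 places that at the last patient's last visit.

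**Non-serious events.** Section 10.2.4 says "Grade 1, 2 and 3 biological events and all other AE/AR have to be reported in the proper CRF AE form", with an exception for events found before dosing. It sets no end date.

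**Late visits.** Under 9.7, PT12 and PT48 include a clinical examination and liver tests. Blood count and creatinine are done at PT12 but not at PT48.

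**The concern.** An endpoint should not claim a longer observation period than the data collection supports. Here the count runs to 48 weeks after treatment, while the duty to collect every adverse event stops at 30 days. The single count would add a period in which all events must be reported to a longer one in which only serious events clearly must be.

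Two consequences follow. First, a low count after day 30 could be read as good late tolerability when it partly reflects the absence of a duty to record. The confidence interval describes sampling variation and cannot correct for that. Second, sites could differ: one may enter a grade 2 ALT rise found at PT12 as an adverse event and another may not, and both would be following the protocol.

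**Working it through.** The plan gives no figure for this point, so the check compares the two windows in days and then reads the reporting rules against each other.

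**Inputs.** Treatment lasts 8 weeks (8.2). The endpoint runs to 48 weeks after treatment (13.9). Full collection ends 30 days after treatment (10.2.2). Post-treatment visits have a window of ±7 days (9.8). Days are counted from the first dose.

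**Window lengths for a patient who completes 8 weeks**
- Treatment: 8 × 7 = 56 days.
- Post-treatment endpoint window: 48 × 7 = 336 days.
- Whole endpoint window: 56 + 336 = 392 days.
- Required collection of all adverse events: 56 + 30 = 86 days.

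**Comparison**
- Whole window: 86/392 = 21.9%.
- Post-treatment part: 30/336 = 8.9%.
- Days in the window without required full collection: 392 − 86 = 306.
- Visits with an adverse event mark: 5 of 7.

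For a patient who stops after t days of treatment, the share is (t + 30)/(t + 336). At t = 28 it is 58/364 = 15.9%, so early stopping lowers it.

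**Why this is not a share of events.** Suppose, purely for illustration, a constant event rate over the 392 days and a fraction f of events captured after day 30. The captured share is (86 + 306f)/392:
- f = 0: 21.9%
- f = 0.5: 61.0%
- f = 1: 100%

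The documents give neither the rate nor f, so the number of events missed cannot be estimated.

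**What is required after day 30**

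| Type of event | Rule | Position after day 30 |
|---|---|---|
| Serious, including grade 4 laboratory | 10.1.3, 10.2.1, 10.2.2 | Notifiable; active enquiry ambiguous |
| Grade 1 to 3 laboratory | 10.2.4, with the period from 10.2.2 | Some tests done; no duty to record as an adverse event |
| Non-serious clinical | 10.2.4, with the period from 10.2.2 | Examination done; no duty to record as an adverse event |

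Section 10.2.4 says how to report; 10.2.2 is the section that sets the period. In 9.7 the 30-day limit in the interview item is followed by a sentence about medications, so it probably limits medications only. The interview about intercurrent disease would then continue at PT12 and PT48, but nothing says that its findings go on the adverse event form.

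**The case against.** The strongest reply is that late capture is far from absent, and this stands. Serious events stay notifiable, grade 4 laboratory events count as serious, patients are examined at PT12 and PT48, and liver tests continue to PT48. A reader might infer from the blank timetable cells that nothing is collected after day 30. The documents do not support that.

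A reader might also infer that late serious events are picked up only passively. That goes too far as well. The release from active monitoring applies only once the trial has ended, which implies that some monitoring is expected until then, and 10.2.1 has no time limit. Against this, the preceding sentence of 10.2.2 makes reporting depend on the investigator's awareness. The text is ambiguous on serious events, and neither reading brings back non-serious or grade 1 to 3 events.

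A third reply is that the time shares say little about lost safety information. This is fair. The dated laboratory signal in 8.2.3, ALT elevation, had a mean onset of 10 weeks and a range of 6 to 12 weeks, and 86 days is 86/7 = 12.3 weeks. Those data come from other trials and are only indicative, but they argue against treating the 306 uncovered days as a matching loss of signal.

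Finally, the endpoint is descriptive, in a 30-patient single-arm pilot, and onset dates on the event forms would allow a split at day 30 at analysis. That limits the weight of the point. It does not remove the conflict, because the plan specifies no split. The amendment log records the 30-day rule as added at version 4.0, which may explain how the mismatch arose, but both statements are in current text.

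**Conclusion.** The inconsistency is real and should be fixed. The endpoint's 48-week window and the 30-day collection rule cannot both describe the same complete count. The certain gap is in non-serious and grade 1 to 3 events after day 30; for serious events the gap is an ambiguity about active enquiry.

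Its size is 306 of 392 days for a patient who completes 8 weeks, with required full collection over 22% of the window. It would be wrong to infer that 78% of events would be missed, because the documents give no late event rate.

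The conclusion rests on two readings: that 10.2.2 sets the period for the reporting duties in 10.2.4, and that the 30-day limit in 9.7 applies to medications. If that limit also covers the interview, the gap is wider.

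One descriptive secondary endpoint is affected. The primary endpoint, its precision and the sample size are not.

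**What to change.** Reconcile the passages to one window. The documents do not show which was intended, so the sponsor must choose.

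**Option 1: shorten the endpoint.** In the synopsis, 6.2 and 13.9, restate it as adverse clinical and biological events from first dose to 30 days after last dose, and base the CI on that period. Align the safety objectives in the synopsis and 4.2; the 4.2 version also omits biological events. Add a short paragraph to 13.9 that lists later serious events, and PT12 and PT48 laboratory abnormalities graded with Appendix A4, separately and without a 48-week count or CI. The cost is rewording in five places plus that paragraph, with no added visits. The downside is a shorter stated safety window.

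**Option 2: extend collection, if 48 weeks is intended.** Amend 10.2.2, 9.7 and both timetables so that all adverse events are collected at the existing PT12 and PT48 visits. State with the endpoint that biological events at PT48 cover liver tests only, because blood count and creatinine stop at PT12; without this the biological count would still not be uniform. The cost is added CRF work at two visits and long recall: PT12 to PT48 is 336 − 84 = 252 days (36 weeks), or 329 − 91 = 238 to 343 − 77 = 266 days with the visit windows.

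**In either case,** state in 10.2.2 whether serious events between day 30 and PT48 are actively asked for or reported only if known. Either option may need amendment review under 14.5.

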13.2 Sample size determination

Since the study is single-arm, non-comparative in design, the sample size will be based on statistical precision and not a comparative statistical test. The sample size should allow a precision of <30% absolute difference between lower and upper bounds of the Clopper-Pearson 95%CI. The expected SVR12 rate is 80% from previous studies, hence bounds are calculated from point estimates of SVR12 $\geq 80\%$. A total 30 patients are necessary to fulfill the statistical criteria above.

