13.3 Statistical methods

- **Qualitative variables**

Qualitative variables will be described in terms of numbers of patients, percentages and confidence intervals.

- **Quantitative variables**

Quantitative variables will be described in terms of populations, medians, range and interquartile range or means, standard deviations and confidence intervals of the mean.

- **Variables of the type 'Time to onset of an event'**

The risk of the first onset of events of interest will be described in terms of probability of onset and confidence intervals with the Kaplan-Meier method. The date of origin is the date of inclusion in the research and the time to onset is the difference between the date of diagnosis of the event and the date of inclusion.

A graphic representation will be associated with the results of the analyses whenever possible.

- **Software used for the statistical analysis**

The analyses will be done using STATA® software for usual statistical analyses.

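### The safety endpoint is a number of events with a 95% CI but has no denominator, interval method or rule for repeat events; if events were pooled as independent, the interval would be too narrow

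*Combined protocol and SAP*

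**What the plan says.** - **Endpoint.** Section 13.9 (Safety assessment) begins "Number of adverse clinical and biological events that occur during the treatment" and attaches a 95% CI to that number. Section 6.2 and the synopsis have the same definition. The AIDS-defining endpoint has the same form: "Number of AIDS-defining clinical or biological events using CDC classification (95% CI").
- **General methods.** Section 13.3 states: "Qualitative variables will be described in terms of numbers of patients, percentages and confidence intervals". For quantitative variables it offers medians, or means with a confidence interval of the mean. For time-to-event variables it states: "The risk of the first onset of events of interest will be described in terms of probability of onset", by Kaplan-Meier. None of these methods is assigned to the safety endpoint.
- **Named interval method.** Clopper-Pearson is the only one for a proportion, and it is named only for SVR12 (synopsis, 13.1, 13.2).
- **What is counted.** Section 10.2.4 requires grade 1 to 3 biological events on the adverse-event form; for an event present at inclusion, only a worsening is notified. It also says "When several symptoms are linked together (to one pathology), they will not be reported as additional adverse events", but this stands among the instructions for SAE forms. Appendix A4 grades AST, ALT, GGT, alkaline phosphatase and bilirubin on separate lines.
- **Window.** The endpoint counts "events that occur during the treatment and up to 48 weeks after the end of the treatment (95% CI"). Section 10.2.2 ends routine reporting as follows: "Until 30 days following the end of study treatment". The timetables in sections 2 and 9.1 agree with 10.2.2. SAEs after treatment are reported if the investigator becomes aware of them.

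**The concern.** A proportion of patients has an obvious unit and denominator. A number of events has neither until the plan supplies them. One patient can contribute several events: liver tests are taken at every scheduled visit except where recent results replace screening, and each is graded on its own line. Two analysts with the same data could therefore report different intervals, and one natural choice, a Poisson interval on the total, is valid only if events are independent.

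The second cost does not depend on any interval. A total over 30 people does not say how many had an event, and that is what a reader of a tolerability study wants to know.

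**Working it through.** **1. The plan's figures.** The plan gives no figure for the safety interval, so there is none to reproduce. Its one input here is the sample size: "A total 30 patients are necessary to fulfill the statistical criteria above" (13.2, for SVR12 precision).

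**2. Assumed inputs.** Events per patient and their spread are not in the documents. I take a mean m = 2 and a variance-to-mean ratio φ from 1 (independent events) to 4. Counts per patient are negative binomial with dispersion k, where φ = 1 + m/k.

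**3. Two intervals for the same data.**
- Pooled: exact Poisson limits for a total X, χ²(0.025; 2X)/2 to χ²(0.975; 2X+2)/2.
- Patient as unit: mean count ± t(0.975; 29) × SD/√30, which is the confidence interval of the mean that 13.3 allows for quantitative variables.

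Simulated coverage, 30 patients, m = 2, 40,000 runs per row:

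| φ | Poisson on pooled total | t interval on patient counts |
|---|---|---|
| 1 | 96% | 95% |
| 1.2 | 94% | 95% |
| 1.5 | 91% | 94% |
| 2 | 86% | 93–94% |
| 3 | 77% | 93% |
| 4 | 70% | 92% |

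Over a wider assumed range (m = 1 to 3; k = 2, 1 and 0.5), Poisson coverage runs from 90% down to 55%. Clopper-Pearson on patients with at least one event stays between 95.7% and 98.6% in every setting, including those without clustering.

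**4. Width.** The standard error of the total grows by √φ. With 60 events in 30 patients, the exact Poisson interval is 45.8 to 77.2. At φ = 2 an approximate interval is 60 ± 1.96 × √(2 × 60) = 60 ± 21.5, that is 38.5 to 81.5.

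**5. What the count hides.** Suppose 15 events occur. The Poisson interval on the total is 8.4 to 24.7 however they are distributed. If they fall in 15 patients, 15/30 is 50% (Clopper-Pearson 31.3% to 68.7%). If they fall in three patients, 3/30 is 10% (2.1% to 26.5%).

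**6. Window.** Endpoint: treatment plus 48 weeks. Routine collection: consent to 30 days after treatment. Liver tests continue to PT48 and blood count and creatinine to PT12, but in both timetables the adverse-event row stops at PT4. From 30 days to 48 weeks the count would rest on SAEs that happen to become known and on whatever is derived from laboratory values.

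**The case against.** A reader might infer that the plan treats correlated events as independent and that its interval will be too narrow. The documents do not support that. They name no Poisson interval, no pooling and no independence assumption. A confidence interval on event counts does not require independence: per-patient counts, a robust variance, a negative binomial model or a patient-level bootstrap all avoid it. The methods in 13.3 are patient-level, and the interval of the mean listed there covers about 92% to 95% in the table above. This part of the objection stands, and narrowness is therefore conditional. It does not close the gap, because 13.3 is not tied to this endpoint and the reinfection endpoint in the same list counts patients explicitly, so events cannot simply be read as patients.

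Three further inferences go too far:

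- **One liver episode as five events.** Section 8.2.3 says bilirubin rises were typically not associated with ALT rises, puts ALT rises from normal to above 5 times ULN at 13/1690 (under 1%), and 10.2.4 keeps an event already present at inclusion out unless it worsens. Strong clustering is possible but not established.
- **The AIDS-defining line.** It has the same wording, but nothing shows clustering there, and 7.2 excludes patients with stage C opportunistic infections that are active or occurred within 6 months before baseline.
- **Merging the liver tests of one sample.** This cannot change the number of patients with at least one biological event, so it is not needed.

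It is also fair that the safety objective is descriptive, and that 11.2.3 gives the DSMB a clinical judgement rather than a formal stopping rule. No decision hangs on this interval.

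**Conclusion.** The point holds as an underspecified and poorly chosen parameter. The denominator, interval method and handling of repeat events are missing in all three places where the endpoint is defined. The loss of coverage, from about 94% to about 70%, arises only if the pooled count is given a Poisson interval, and it rests on assumed values (mean 2, variance-to-mean ratio 1.2 to 4) that the documents do not supply. With less clustering the loss is small. The failure to show how many patients were affected needs no assumption. The consequence is limited to how precisely and how clearly tolerability is reported. It is still worth correcting, because tolerability is in the title and the remedy costs almost nothing. The conflict between the 48-week and 30-day windows is a direct contradiction in the text and does not depend on any of these calculations.

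**What to change.** 1. In the synopsis, 6.2 and 13.9, make the safety parameter the number and percentage of patients with at least one event: any event, grade 3–4, serious, leading to treatment stop, and each graded laboratory abnormality. Give each the Clopper-Pearson 95% CI already used for SVR12, and state the denominator.
2. Give event counts descriptively without an interval. If an event rate is wanted, define the follow-up time and use an interval that takes the patient as the unit (robust variance, negative binomial or patient-level bootstrap).
3. Reconcile the 48-week window in the endpoint with the 30-day collection period in sections 2, 9.1 and 10.2.2, so that the period analysed is the period in which events are collected.

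Items 1 and 2 are wording changes with the same data and software. The cost of item 3 depends on how the passages are reconciled. The downside is that the intervals no longer describe the total event count and may be wider.
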